4.4 Early study termination

The study can be terminated at any time for any reason by Novartis. Should this be necessary, the patient should be seen as soon as possible and the same assessments should be performed as described in [Table 7-1](#) for a prematurely withdrawn patient. The investigator may be informed of additional procedures to be followed in order to ensure that adequate consideration is given to the protection of the patient's interests. The investigator will be responsible for informing IRBs and/or ECs of the early termination of the trial.

5 Population

5.1 Patient population

The study population will consist of patients with persistent or recurrent Cushing's disease or patients with de novo Cushing's disease that are not considered candidates for pituitary surgery (poor surgery candidates, surgically unapproachable tumor, patients with no visible pituitary tumor, patients who refuse surgery). A confirmed Cushing's disease diagnosis is required.

The investigator or designee must ensure that only patients who meet all the following inclusion and none of the exclusion criteria are offered enrollment in the study.

5.2 Inclusion criteria

Patients eligible for inclusion in this study have to meet **all** of the following criteria:

1. Written informed consent obtained prior to any screening procedures
2. Male or female patients aged 18 years or greater
3. Patients with confirmed diagnosis of Cushing's disease as evidenced by
 - mean urinary free cortisol of three 24-hour urine samples collected during the 3-week screening period above the upper limit of the laboratory normal range
 - morning plasma ACTH within the normal or above normal range
 - either MRI confirmation of pituitary adenoma (greater than or equal to 0.6 cm), or inferior petrosal sinus gradient >3 after CRH stimulation for those patients with a microadenoma less than 0.6 cm*, or for patients who have had prior pituitary surgery, histopathology confirming an ACTH staining adenoma. (* if IPSS had previously been performed without CRH (e.g. with DDAVP), then a central to peripheral pre-stimulation gradient > 2 is required. If IPSS had not previously been performed, IPSS with CRH stimulation is required)
4. Patients with de novo Cushing's disease must not be considered as candidates for pituitary surgery (i.e. poor surgical candidates, surgically unapproachable tumors, patients with no visible pituitary tumor, patients who refuse to have surgical treatment)
5. Karnofsky performance status >60 (i.e. requires occasional assistance, but is able to care for most of his personal needs)

6. For patients on previous medical treatment for Cushing's disease the following washout periods must be completed before screening assessments are performed
 - Inhibitors of steroidogenesis (e.g. ketoconazole, metyrapone, rosiglitazone): 1 week
 - Dopamine agonists (e.g. bromocriptine, cabergoline): 4 weeks
 - Mitotane: 6 months
 - Octreotide LAR and Lanreotide autogel: 8 weeks
 - Lanreotide SR: 4 weeks
 - Octreotide (immediate release formulation): 1 week
 - Glucocorticoid receptor inhibitor (mifepristone): 4 weeks

5.3 Exclusion criteria

Patients eligible for this study must not meet **any** of the following criteria:

1. Radiotherapy of the pituitary <4 weeks before screening or patient who has not recovered from side effects
2. Patients with compression of the optic chiasm causing acute clinically significant visual field defect
3. Patients with Cushing's syndrome due to ectopic ACTH secretion
4. Patients with hypercortisolism secondary to adrenal tumors or nodular (primary) bilateral adrenal hyperplasia
5. Patients who have a known inherited syndrome as the cause for hormone over secretion (i.e. Carney Complex, McCune-Albright syndrome, MEN-1)
6. Patients with a diagnosis of glucocorticoid-remedial aldosteronism (GRA)
7. Patients who have undergone major surgery within 1 month prior to screening
8. Patients with known gallbladder or bile duct disease, acute or chronic pancreatitis (patients with asymptomatic cholelithiasis and asymptomatic bile duct dilation can be included)
9. Diabetic patients whose blood glucose is poorly controlled as evidenced by $\text{HbA}_{1\text{C}} > 8\%$
10. Patients who have clinically significant impairment in cardiovascular function or are at risk thereof, as evidenced by
 - congestive heart failure (NYHA Class III or IV), unstable angina, sustained ventricular tachycardia, clinically significant bradycardia, high grade AV block, history of acute MI less than one year prior to study entry
 - QTcF >450 msec at screening
 - History of syncope or family history of idiopathic sudden death
 - Risk factors for Torsades de Pointes such as uncorrected hypokalemia, uncorrected hypomagnesemia, cardiac failure
 - Concomitant disease(s) that could prolong the QT interval such as autonomic neuropathy (caused by diabetes or Parkinson's disease), HIV, cirrhosis, uncontrolled hypothyroidism, concomitant medication(s) with known risk for TdP
11. Patients with liver disease or history of liver disease such as cirrhosis, chronic active hepatitis B and C, or chronic persistent hepatitis, or patients with ALT or AST more than

2 x ULN, serum creatinine >2.0 x ULN, serum bilirubin >1.5 x ULN, serum albumin < 0.67 x LLN at screening

12. Patients who have any current or prior medical condition that can interfere with the conduct of the study or the evaluation of its results, such as

- History of immunocompromise, including a positive HIV test result (Elisa and Western blot). An HIV test will not be required, however, previous medical history will be reviewed
- Presence of active or suspected acute or chronic uncontrolled infection
- History of, or current alcohol misuse/abuse in the 12 month period prior to screening

13. Female patients who are pregnant or lactating, or are of childbearing potential and not practicing a medically acceptable method of birth control. If a woman is participating in the trial then one form of contraception is sufficient (pill or diaphragm) and the partner should use a condom. If oral contraception is used in addition to condoms, the patient must have been practicing this method for at least two months prior to screening and must agree to continue the oral contraceptive throughout the course of the study and for one month after the study has ended. Male patients who are sexually active are required to use condoms during the study and for three month afterwards as a precautionary measure (available data do not suggest any increased reproductive risk with the study drugs)

14. Patients who have participated in any clinical investigation with an investigational drug within 1 month prior to screening or patients who have previously been treated with pasireotide

15. Known hypersensitivity to somatostatin analogues

16. Patients with a history of non-compliance to medical regimens or who are considered potentially unreliable or will be unable to complete the entire study

17. Patients with presence of Hepatitis B surface antigen (HbsAg)

18. Patients with presence of Hepatitis C antibody test (anti-HCV)

6 Treatment

6.1 Investigational treatment, other treatment, supportive treatment

The investigational study drug used in the course of this trial is pasireotide for subcutaneous (s.c.) administration.

6.1.1 Dosing regimen

The starting dose will be:

- [Applicable for countries in the European Union] 600 µg b.i.d. (twice daily) in all patients also including the ones with impaired glucose metabolism with the option to increase the dose to 900 µg b.i.d. if the patient is not controlled (i.e. 24h-mean UFC levels above the upper limit of normal) at earliest after 2 months of treatment provided the 600 µg b.i.d dose is well tolerated by the patient. However ongoing patients in the study at the time of approval of amendment 3 will continue on their current dose.

- [Applicable for countries outside the European Union] 900 µg b.i.d. (twice daily). The initial dose for patients with impaired glucose metabolism will be 600 µg b.i.d

6.1.2 Treatment duration

Patients will be treated until the drug is approved for commercial use and reimbursed in each respective country or until 31 December 2015 (until 31 December 2016 for sites in South Korea and Brazil), whichever occurs first. Should pasireotide not be approved for commercial use and reimbursed in each respective country, Novartis will have a local transition plan in order to ensure that all trial patients will still have access to the study medication without any delay in their treatment.

6.2 Dose escalation guidelines

[Applicable for countries in the European Union] Refer to corresponding paragraphs in [Section 6.2.1](#).

6.2.1 Dose modifications

Uncontrolled disease [Applicable for countries in the European Union]:

If the patient is not controlled with pasireotide 600 µg b.i.d (i.e. 24h-mean UFC levels above the upper limit of normal) after 2 months of treatment, the dose will be increased to 900 µg b.i.d provided the 600 µg b.i.d dose is well tolerated by the patient. Dose increase will be done as soon as UFC results from Visit 7 are available or at the latest at Visit 8.

In case the dose cannot be increased to 900 µg b.i.d after Visit 7 or at the latest at Visit 8 due to tolerability issues, the dose should be considered to be increased at subsequent visits provided 24h-mean UFC levels are still above the upper limit of normal and safety issues have been resolved.

If patients have been controlled with the 600 µg b.i.d dose but are no longer controlled (i.e. 24h-mean UFC levels above the upper limit of normal) with this dose at any time in the study after Visit 7, the dose will be increased to 900 µg b.i.d provided the 600 µg b.i.d dose is well tolerated by the patient. Dose increase will be done as soon as UFC results are available or at the latest at the next visit.

Disease control:

Patients having sustained mean 24h-UFC normalization evidenced by at least 2 consecutive normal 24h-mean UFC may have their pasireotide dose reduced, at the discretion of the investigator.

- Patients receiving 900 µg s.c. b.i.d., will be reduced to receive 600 µg s.c. b.i.d.
- Patients receiving 600 µg s.c. b.i.d., will be reduced to receive 300 µg s.c. b.i.d.

Should UFC levels increase above the upper limit of normal after down-titration, the dose should be up-titrated to the previous one.

Safety issues:

For patients who are unable to tolerate the protocol specified dose level, guidelines described in [Table 6-1](#) have to be followed.

At any time during the study, patients with an early morning (between 8 and 10 am) serum cortisol < 3 µg/dl and a mean 24h-UFC measurement < LLN or symptoms suggestive of hypoadrenalinism (e.g. postural hypotension, nausea, and abdominal pain) in association with a mean 24h-UFC measurement < LLN should have their dose reduced by 300 µg b.i.d. Patients should return to their previous dose once the tolerability issue resolves.

Any dose changes must be recorded on the Dosage Administration Record.

6.2.1.1 Follow-up for toxicities

Hyperglycemia

Hyperglycemia is known to be associated with the treatment of somatostatin analogues (SSA). Clinical studies of pasireotide in healthy volunteers and in patients with Cushing's disease, acromegaly or carcinoid syndrome have reported transient, asymptomatic increases in fasting and postprandial glucose levels. Two clinical studies have been conducted ([\[SOM230B2216\]](#) and [\[SOM230B2124\]](#)) in healthy volunteers to further understand the mechanism of pasireotide-induced hyperglycemia and to evaluate the potential clinical utility of anti-diabetes agents in the management of pasireotide-induced hyperglycemia. Data from ([\[SOM230B2216\]](#) study indicate that pasireotide decreases insulin secretion, particularly in the postprandial period, as well as the GLP-1/GIP secretion. Results from [\[SOM230B2124\]](#) study suggest that the incretin-based therapies (GLP-1 analogues and DPP-4 inhibitors) may have the best potential to manage the hyperglycemia associated with pasireotide. Some patients in [\[SOM230B2305\]](#) required insulin to treat their hyperglycemia.

Monitoring of blood glucose:

[figure not shown]
The principal investigator is to educate the patient on the signs and symptoms of hyperglycemia. In addition to the laboratory evaluation of blood glucose level at the regular scheduled visits ([Table 7-1](#)), patients are asked to self-monitor their blood glucose using a home glucometer provided by Novartis at least 3 times per week for the first month of pasireotide treatment. If the patient does NOT have any fasting values above 100mg/dL, monitoring can be decreased to at least 2 times per week for months 2 and 3 and 1 time every 2 weeks for months 4 through 7. If glucose levels remain normal (below 100mg/dL), monitoring is at the investigator's discretion after month 7. If any values are observed above 100 mg/dL, the guidelines in figure below are to be followed. These guidelines are based on the current recommendations from the 2012 ADA and EASD aiming at a glycemic treatment goal of FPG <130 mg/dL (<7.2 mmol/L). Appropriate actions such as initiation of anti-hyperglycemic therapy (and referral to diabetes specialist) are to be taken by the investigator as outlined on [Figure 6-1](#). If fasting blood glucose values dictate initiation of anti-hyperglycemic treatment (i.e., confirmed >130 mg/dL by self-monitoring), a fasting plasma glucose sample using the local laboratory is to be collected prior to initiation of anti-hyperglycemic treatment. If a patient has a dose increase, monitoring for hyperglycemia should follow the recommendations for the first month of treatment and continue as presented above for subsequent months.

It is recommended that the patients be encouraged to keep a diary for their blood glucose for appropriate management throughout the study and present the collected data to their physician/diabetes specialist for evaluation. This data will not be collected by the sponsor.

In addition to self-monitoring, fasting plasma glucose and HbA1c will be collected at study visits per [Table 7-1](#). Close and frequent monitoring of blood glucose is needed during pasireotide treatment. Intervention for hyperglycemia is to be implemented in any patient meeting any of the following criteria: FPG > 130 mg/dL or HbA1c \geq 6.5 %.

Patients with FPG > 160 mg/dL or HbA1c > 7.5% despite adjustment of antidiabetic therapy should be referred to a diabetes specialist (or earlier per investigator's judgment).

Figure 6-1 Fasting self-monitoring blood glucose (SMBG) guidelines

[figure not shown]
QT prolongation:

If at any visit a QTcF > 500 msec is observed, triplicate ECGs, each 2-3 min apart need to be taken approximately 1 hour after the initial ECG. The mean QTcF from the triplicate ECGs will be determined. If the mean QTcF is > 500 msec, the patient has to discontinue the study medication until a cardiologist has re-evaluated the ECG. The re-evaluation is required to be done as soon as practical but within 7 days of the initial finding of abnormal ECG. If the cardiologist confirms a mean QTcF > 500 msec, the patient will be withdrawn from the study. Otherwise and if the cardiologist confirms that at least one ECG shows QTcF > 480 msec, the cardiac assessments described for a confirmed QTcF > 480 msec are to be followed.

If at any visit a $480\text{msec} < \text{QTcF} \leq 500\text{msec}$ is observed for the first time for a patient at a given dose level, the following steps are to be taken (as described in [Figure 6-2](#)):

- A cardiology consultation must be sought as soon as practical but within 7 days of the initial finding of abnormal ECG and the cardiologist is to re-evaluate the ECG
 - If a $\text{QTcF} > 480\text{msec}$ is NOT confirmed, no further action is to be taken
 - If a $\text{QTcF} > 480\text{msec}$ is confirmed, a cardiologist must perform a thorough examination (such as reviewing baseline ECG, concurrent medications and performing a cardiovascular examination (including at least a cardiac auscultation) to assess the patient for cardiovascular risk factors).
 - If based upon the assessment by the cardiologist, the investigator considers that there is an acute cardiovascular safety risk and that the patient should not continue with study medication, the patient is to be discontinued immediately (discontinuation criteria to be followed).
 - If following the examination by the cardiologist, the investigator considers that there is not an acute cardiovascular safety risk and that the patient could continue to receive study medication, a 24-hr Holter-ECG is to be recorded as soon as practical but within 7 days after the initial finding of abnormal ECG. The Holter ECG is to be started 30 minutes prior to an injection of study medication.
 - The results of the ECGs, cardiac examination, Holter ECG and the recommendations by the cardiologist are to be evaluated by the Investigator to determine whether the patient should continue in the trial or not (discontinuation criteria to be followed)

Figure 6-2 QT Prolongation Monitoring Flow Chart

Hepatic safety management:

If any of the criteria below are observed at any scheduled or unscheduled visit the sponsor should be notified immediately upon awareness.

- ALT or AST $> 3 \times \text{ULN}$ and Total Bilirubin $\geq 2 \times \text{ULN}$
- ALT or AST $> 5 \times \text{ULN}$ and $\leq 8 \times \text{ULN}$
- ALT or AST $> 8 \times \text{ULN}$

The following should be performed immediately within **72 hours** of awareness of the abnormality:

- Perform liver-directed medical history and physical examination (i.e. assess occupational hazards, concomitant medications including OTC meds, inter-current illness, etc)
- Liver chemistry tests: ALT, AST, total bilirubin, (fractionate to direct/indirect bilirubin if total bilirubin is $> 2.0 \times \text{ULN}$), Albumin, PT (INR), ALP, and GGT
- Perform hepatitis screen: anti-HAV, IgM (to confirm acute Hepatitis A), HbsAg, Anti-HBc, anti-HCV (if positive, PCR viral load should be assessed), Anti-HEV, ANA antibodies, anti-smooth muscle anti-bodies, CMV and EBV
- Perform abdominal ultrasound (liver and biliary tree)

Liver chemistry tests (LFTs) should be monitored every **3-4 days** until resolution or return to baseline status.

Patients or subjects may need to be discontinued if the abnormal liver function criteria are met upon LFT retesting (See discontinuation criteria [Section 7.1.3.1](#)). Progress reports of the event should be maintained until resolution or stabilization (i.e. no further elevation after 2 consecutive assessments).

[figure not shown]
For ALT or AST $> 5 \times \text{ULN}$ and $\leq 8 \times \text{ULN}$, the following must occur (in addition to the safety follow up procedures noted above)

- Study medication should be temporarily interrupted and liver chemistry tests monitored every **3-4 days** until resolution or return to baseline.
- If resolution or return to baseline does not occur after 2 weeks, the patient should be discontinued.
- If ALT or AST return to less than $5 \times \text{ULN}$ study drug can be resumed and patient can continue study per protocol.
- If ALT or AST rises above $5 \times \text{ULN}$ anytime after study drug is resumed, then study drug should be discontinued immediately.

If any of these criteria are met and deemed an adverse event by the investigator, the event must be recorded on the Adverse Event (e) CRF page; if the event is deemed serious by the investigator, then proceed with completing the SAE form. In addition, any significant findings from the physical examination should be recorded on the Adverse Event (e) CRF page.

[REDACTED]

Figure 6-3 LFT management algorithm

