7.1.3.1 Criteria for premature patient withdrawal

Patients **may** voluntarily withdraw from the study or be dropped from it at the discretion of the investigator at any time.

Patients **must** be withdrawn from the study if any of the following occurs:

- Patients experiencing unacceptable drug-related toxicity (as described in [Table 6-1](#))
- Uncontrolled diabetes mellitus (DM), consistently high capillary glucose values in excess of 275 mg/dL (15.5 mmol/L), FPG \geq 240 mg/dL (13.3 mmol/L) or HbA_{1c} value \geq 10 % despite prior appropriate management and prior dose adjustment of the study drug,
- Patients experiencing adverse events in QTc:
 - a confirmed QTcF $>$ 480 msec and discontinuation recommended by a cardiologist, or
 - Mean QTcF $>$ 500 msec measured by triplicate ECGs and confirmed by a cardiologist
 - Significant arrhythmia findings from Holter monitoring such as:
 1. Any ventricular or supra-ventricular tachyarrhythmia associated with symptoms of hemodynamic compromise
 2. Sustained ventricular tachycardia ($>$ 30 sec) irrespective of symptoms
 3. Recurrent non-sustained VT (\geq 3 beats) during any 24-hour monitoring period
 4. Torsades de Pointes (TdP)
 5. Cardiac arrest
 6. Pause $>$ 5 seconds
 7. Second or third degree AV block
 - New occurrence of clinically significant/symptomatic bradycardia, or
 - Increased risk of QT prolongation by use of medications with known risk of TdP, or
 - Hypokalemia ($<$ 3.5 mmol/L) or hypomagnesaemia ($<$ 0.5 mmol/L) confirmed by repeat testing that is either a new finding or accompanied by vomiting or diarrhea and not corrected by treatment.
- Evidence of hypoadrenalinism: defined as an early morning (between 8 and 10 am) serum cortisol $<$ 3 μ g/dL and a mean 24h-UFC measurement $<$ LLN or symptoms suggestive of

hypoadrenalinism (e.g. postural hypotension, nausea, and abdominal pain) in association with a mean 24h-UFC measurement < LLN, which persist after drug dose adjustment

- Lack of efficacy: consistently elevated mean 24h-UFC level and lack of clinical benefit after ≥ 3 months treatment
- Pregnancy
- Patient experiencing
 - ALT or AST $> 3 \times$ ULN and Total Bilirubin $\geq 2 \times$ ULN and ALP $< 2 \times$ ULN
 - ALT or AST $> 5 \times$ ULN and $\leq 8 \times$ ULN persistent for more than 2 weeks
 - ALT or AST $> 8 \times$ ULN

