7.2.2.5 Cardiac assessments

7.2.2.5.1 Electrocardiogram (ECG)

[figure not shown]
A 12-lead ECG will be performed at the sites, in lying position, at all indicated visits as per [Table 7-1](#).

[figure not shown]
All ECGs should include all 12 standard leads and a Lead II rhythm strip of at least a 10-second duration. The ECGs will be evaluated locally.

Interpretation of the tracing must be made by a qualified physician and documented on the ECG CRF page. Each ECG tracing should be labeled with the study number, patient initials (where regulations permit), patient number, date, and kept in the source documents at the study site. Clinically significant abnormalities present when the patient signed informed consent should be reported on the Medical History CRF page. Clinically significant findings must be discussed with the Medical Monitor prior to enrolling the patient in the study. New or worsened clinically significant findings occurring after informed consent must be recorded on the Adverse Events CRF page. In case of confirmed QTcF $>$ 480msec, a Holter ECG will be required for patients continuing in the study (described in [Section 6.2.1.1](#)).

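### A first QTcF reading of 480–500 msec that the cardiologist does not confirm can use up the mandatory cardiology review at that dose level

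*Protocol*

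**What the plan says.** Protocol section 6.2.1.1 (QT prolongation) sets separate rules for two bands of QTcF.

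- **480 < QTcF ≤ 500 msec.** The rule applies when such a value "is observed for the first time for a patient at a given dose level, the following steps are to be taken". The first step is a cardiology consultation, with re-evaluation of the ECG, within 7 days. If a QTcF above 480 msec "is NOT confirmed, no further action is to be taken". If it is confirmed, the cardiologist examines the patient, and a 24-hour Holter recording follows if the patient is to stay on drug.
- **Above 500 msec.** The rule begins "If at any visit a QTcF > 500 msec is observed, triplicate ECGs" and is not limited to a first occasion or to a dose level.

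On reading the tracings, section 7.2.2.5.1 says "The ECGs will be evaluated locally" and "Interpretation of the tracing must be made by a qualified physician". It also requires a Holter ECG for patients who continue after a confirmed QTcF above 480 msec, and refers back to 6.2.1.1. The matching withdrawal criterion in 7.1.3.1 needs a confirmed QTcF above 480 msec and "discontinuation recommended by a cardiologist".

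On dose, a footnote to Table 6-1 exempts QT prolongation from dose reduction. For EU patients not controlled on 600 µg, section 6.2.1 says "Dose increase will be done as soon as UFC results from Visit 7 are available or at the latest at Visit 8". For a patient whose UFC rises above normal again after down-titration, "the dose should be up-titrated to the previous one".

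**The concern.** A limit of one full work-up per dose level is reasonable once a prolonged QTcF has been confirmed and assessed. The difficulty is that the limit is attached to the first observed value, and observation comes before confirmation in the rule. A cardiologist who rejects one tracing has ruled on that tracing only. The decision says nothing about a later one, after longer exposure or a change in electrolytes or co-medication. On the literal text, the later tracing need not go to a cardiologist.

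QT-prolongation is a listed event of special interest (section 8.2.2). The first thorough QT study found a peak difference from placebo of 17.5 msec, although at 1950 µg b.i.d., which is above the doses used here (section 1.2.2). There is no data monitoring committee (section 8.6). A cardiology review that is mandatory for the first reading becomes a matter of site judgement for the second.

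**Working it through.** The plan gives no figure to reproduce. The check is a trace through the rules, then a count of the ECGs exposed to the gap.

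**Trace at one dose level D**

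1. Reading 1 is between 480 and 500 msec. It is the first observed at D, so the consultation is mandatory.
2. The cardiologist does not confirm a QTcF above 480 msec. No further action follows.
3. Reading 2 at D is again between 480 and 500 msec. It is no longer the first observed at D, so the mandatory consultation is not triggered.
4. No dose reduction is required for QT prolongation, so the patient can stay at D. A dose level not used before opens a fresh trigger. A return to D does not clearly do so, and section 6.2.1 provides for such returns.

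**Do other rules catch reading 2?**

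| Rule | Limited to first reading? | What it needs | Covers an unconfirmed second reading? |
|---|---|---|---|
| Above 500 msec (6.2.1.1) | No | QTcF > 500 msec | No, reading 2 is below this |
| Holter (7.2.2.5.1) | No | Confirmed QTcF > 480 msec | Only if someone chooses to seek confirmation |
| Withdrawal (7.1.3.1) | No | Confirmed QTcF > 480 msec and a cardiologist's recommendation | Same |

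The visible text describes two routes to confirmation: the first-observation consultation, and the branch for values above 500 msec. Reading 2 enters neither.

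**Scheduled ECGs remaining after an unconfirmed reading at Week 1 (Visit 3)**

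Inputs: visits and ECGs from Protocol Table 7-1, with an ECG at each treatment visit; visit numbers beyond Visit 13 from SAP Table 4-1.

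- EU patient raised to 900 µg after Visit 7: Visits 4 to 7, 7 − 4 + 1 = 4. Raised at Visit 8: Visits 4 to 8, 8 − 4 + 1 = 5.
- Dose unchanged through Week 48: Visits 4 to 13, 13 − 4 + 1 = 10.
- Dose unchanged through Week 156: Visits 4 to 22, 22 − 4 + 1 = 19. This is an upper bound, not an estimate.

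**How long a change to version 6 could act**

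- From 13 November 2015 to 31 December 2016: 366 + 48 = 414 days; 414 / 7 = 59.1 weeks. This applies only to sites in South Korea and Brazil.
- Elsewhere treatment ends by 31 December 2015: 17 + 31 = 48 days.
- Patient already past Week 24, visits every 84 days: 414 / 84 = 4.9, about 5 ECGs.
- Patient starting on 13 November 2015: Week 48 (day 336) falls inside the 414 days and Week 60 (day 420) outside, so 10 ECGs follow Week 1.

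**The case against.** The strongest reply is that the phrase can be read differently. If the cardiologist's re-read does not support a QTcF above 480 msec, one may say that no such value has yet been observed at that dose, and that taking no further action closes only that episode. The rule also refers to Figure 6-2, which is not visible in the available text and is where a loop for repeat readings might appear.

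The alternative reading strains a rule in which a value is first observed and only then confirmed or not. If two sites can read a safety trigger in opposite ways, the sentence needs clarifying in any case. The point about Figure 6-2 stands as a limit on certainty.

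The remaining safeguards are real. A qualified physician interprets every tracing. New clinically significant findings are recorded as adverse events. QT-prolongation is notified in the same manner as an SAE. Entry excludes QTcF above 450 msec and risk factors for torsades. Sites may refer or withdraw a patient at any time. These reduce the risk, but none of them makes the second cardiology re-read mandatory.

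It is also fair to say that counts of ECGs do not measure harm. Harm needs a first reading in a 20 msec band that is not confirmed, a later true reading in the same band at the same dose, a site that applies the wording literally, and an investigator who does not refer. The documents give no frequency for any of these steps.

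**Conclusion.** The concern holds on the visible text. After one unconfirmed local reading of 480–500 msec, cardiology review of a later reading in that band at the same dose is discretionary, and the two rules that could act on it wait for a confirmation that nothing then requires.

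The conclusion assumes the literal meaning of first observation and that Figure 6-2 adds no reset; confidence is therefore moderate. It is limited to the 480–500 msec band, and the ECG counts assume the patient stays at one dose between the stated visits. The number of patients affected cannot be derived and is probably small under version 6, given the short remaining treatment period. No statistical estimate or analysis is affected. It is a patient-safety wording point that should be corrected because the correction is cheap.

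**What to change.** Reword the trigger in section 6.2.1.1, and in Figure 6-2 if the figure repeats it, along these lines: the steps apply to any reading of 480 < QTcF ≤ 500 msec, unless a QTcF above 480 msec has already been confirmed and worked up for that patient at that dose level. A reading that the cardiologist did not confirm then does not count as the first occurrence, and a return to an earlier dose causes no difficulty. The once-per-dose limit stays in place after a confirmed and completed work-up.

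The cost is one sentence and a few additional cardiology re-reads of tracings already recorded. Examination and Holter recording follow only if the re-read confirms a QTcF above 480 msec.
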